inferior occipital gyrus, the middle occipital gyrus (and sulcus), the superior occipital gyrus, the cuneus, the lingual gyrus, the occipital pole, and the calcarine sulcus. CT will be investigated more specifically inside visual areas, namely V1 (BA17) – primary visual area, V2 (BA18) – secondary visual area, and V5/MT – visual area, middle temporal, by using an atlas from the Martinos Center for Biomedical Imaging (US) and the Institute of Neurosciences and Biophysics (Germany) (<http://surfer.nmr.mgh.harvard.edu/fswiki/BrodmannAreaMaps>). In order to examine if vision rehabilitation will result in changes in CT, we will examine by calculating percentage difference in extracted CT values for each of the above-mentioned visual regions pre- and post- reading rehabilitation. Differences between groups or between regions pre- and post-intervention will be considered significant at $p < 0.05$ after correction using false discovery rate.

Limitations & Mitigation Strategies:

Given the logistics of having the reading intervention delivered through services that are regulated by the Quebec Ministry of Health, we place our trust in the quality of rehabilitation service delivery without being able to control this aspect of the study; however, we believe that this trust is well deserved, given the quality and type of care provided in Quebec¹¹⁴⁻¹¹⁶. It is likely that a certain number of participants will self-select not to complete the 1-year follow-up or to abandon parts of the recommended intervention tools and techniques. Therefore, we will examine differences in participant characteristics and consider intent-to-treat within the statistical analyses. We expect certain variability in the cognitive status of our participants, as there are no cognitive exclusion criteria. This pragmatic approach to recruitment is chosen intentionally as we speculate that the beneficial effect of reading rehabilitation may become apparent at different levels of magnitude, depending on the cognitive starting point; however, this remains speculation at this point. Our statistical analyses will need to consider this additional source of variability.

Integrated KT strategy: Established collaborations with the Sense-Cog group in Europe (<https://www.sense-cog.eu/>), Envision University in the USA (<https://university.envisionus.com/Home>) and the CCNA KT team provide access to sensory-cognitive-specific KT networks that will facilitate the distribution and implementation of our findings. In addition, we have secured specific iKT collaboration with the Center for Interdisciplinary Rehabilitation Research of Greater Montreal (see support letter), Envision University and the annual Envision Conference in Wichita, Kansas (see support letter). [name], as a visually impaired scientist¹¹⁷ and a team member brings a unique and important KT, equality and inclusion perspective to the project. Our close partnerships to local sensory rehabilitation agencies (represented by [name] and [name]) allow for an ongoing exchange to ensure that the project development remains clinically relevant while allowing us the expand sensory-cognitive health science (see also [name] lab network in Appendix). All collaborators and partners will participate in the development of a *Café scientifique* at project completion in order to disseminate the results at a clinical level. In addition, dissemination and continuing education courses will be developed for Envision University online as well as for Envision Conference in person.

Sex, Gender, Equity, Diversity & Inclusion: Being female has been identified as a risk factor for the development of AMD in some¹¹⁸ but not all studies¹¹⁹; therefore, self-reported gender (binary men/women) will be considered in all analyses for comparison and as a control. We will pay specific attention to the men/women ratio in the sample as recruitment will likely result in a larger number of women who will participate, given their increased lifespan and larger client numbers in vision rehabilitation settings. In addition, contradicting gender differences in openness to the acceptance and use of assistive technology have been reported¹²⁰⁻¹²², which directly impacts on the potential benefit of reading rehabilitation approaches that include electronic magnification (e.g., the use of an iPad^{39,40}). Therefore gender will feature prominently in our statistical analyses.

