Pilot data from our currently funded FRQS project focusing on cognition and AMD indicate correlations between sensory and cognitive variables in the expected directions insofar as individuals with faster reading speeds demonstrated better scores on the Montreal Cognitive Assessment^{57,58}. Given the information reviewed above, the logical direction for our investigation into the functional connection between LV and cognition is to examine the possible effects of reading rehabilitation on the cognitive abilities of LV patients over time. In order to dis-entangle the effects of visual and cognitive impairments in older adults, members of this research team have adapted cognitive tests so they can be administered to individuals with low vision^{59,60}. In parallel, we are also in the process of developing a vision-screening test that can be administered to individuals with various levels of cognitive impairment^{61,62}. This investigation will guide our future research efforts into the improvement of service provision in LV rehabilitation for the purpose of increasing the independence and health of older adults living with LV.

[figure not shown]
The objectives are to:

- Evaluate cognitive functioning and memory before, and 6 and 12 months after low vision reading rehabilitation using magnification in AMD patients, compared to those with dual (vision and hearing) impairments, and age-matched controls
- Correlate participant characteristics with all cognitive outcome variables in order to identify potential mediators, moderators or confounders

Hypotheses:

- Measures of reading effort (self-report and objective reading speed) will be statistically significantly reduced after participants have received strategies and tools to facilitate reading.
- Measures of reading behaviour will be negatively correlated with measures of reading effort (e.g., participants who report less effort will read a greater amount, more frequently and for longer)
- Individuals who demonstrate reduced reading effort and improved reading behaviour will demonstrate improved scores on cognitive tests after 6 months of having received rehabilitation strategies and tools, compared to those whose reading effort remains high or whose reading behaviour remains unchanged. These beneficial effects will be maintained after 12 months.
- Reading measures correlate with cortical thickness (CT) in the visual cortex;

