- There will be reduced CT in the visual cortex in the low vision groups compared to matched controls at baseline
- Reading rehabilitation results in increased CT in the low vision groups, but not in the control group after 12 months.

Ethics Approval has been obtained through the *Comité d'éthique de la recherche* of the *Centre de recherche interdisciplinaire en readaptation du Montreal metropolitan (CRIR#1284-1217)* which is responsible for research protocols involving recruitment from the clinical partners (local sensory rehabilitation centres) within this study: the *CRIR/Centre de réadaptation MAB-Mackay du CIUSSS du Centre-Ouest-de-l'Île-de-Montréal*, and the *CRIR/Institut Nazareth et Louis-Braille du CISSS de la Montérégie-Centre* (see attached letters of support). Additional approvals and modifications (MRI component) will be obtained through the university affiliations of the team members.

Study Design: We will employ a quasi-experimental approach (non-randomized, pre-post intervention study)⁶³, an approach frequently used during the evaluation of health interventions⁶⁴. Specifically, a 3x3 design (3 groups x 3 time points) will allow us to examine whether cognitive performance will change before and after 6 and 12 months of a low vision reading intervention, when comparing LV and dual sensory impaired (DSI) patients to age-matched controls with age-normal vision and hearing⁶⁵. Participants will be audio-recorded throughout several of the tasks to ensure the highest level of precision when inputting and analysing data, and to help reduce the overall testing time. All aspects of the study design and data analysis will be submitted as a stage 1 pre-registered report.

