Sample Size: Effect sizes in vision rehabilitation in the past have ranged from approximately Cohen's $d = .20$ to 2.5 ³⁸. Since there are no existing effect size estimates for cognitive ability in the context of low vision rehabilitation, we are applying these values as a guide line: Using an average value of $d = 1.0$, and converting this value into variance accounted for ($r^2 = .20$ ¹⁰⁵), we can estimate a required sample size. Using a 3x3 (group x time point) within-between design for Analysis of Variance, power analysis using gPower¹⁰⁶ indicates that a sample size of $n = 141$ allows us to detect small effect sizes of .15 or greater, with an alpha of 0.05 and a desired power of .95. We expected an attrition rate of around 10% at each time point, given our previous research with older visually impaired adults^{107,108}. Therefore, a sample of $n = 200$ (to yield 150 patients, 50 controls) should be sufficient for our protocol. This goal is feasible given an average of 3000 new referrals to rehabilitation in Montreal per year.

Data Collection

Time 1 – Pre-Reading Rehabilitation: Participants will complete the questionnaires, hearing, reading and cognitive assessment components between their initial global intake exam and their first rehabilitation appointment. This period can span anywhere around 3 months, depending on waiting lists, and we will track whether any substantial changes in health occurred during this period that could influence eligibility or data collection.

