Time 2 – 6-Months and Time 3 – 12-Months Follow-Up: Six and 12 months after the initial rehabilitation appointment, the research assistant will meet with each participant (at home or in the lab, according to their preference) in order to repeat the experimental protocol, and all reading, cognitive and hearing measures will be administered each time. Throughout the period of the protocol, data from the rehabilitation chart will be extracted as it becomes available, with the final data collection concluding after the 12-month follow-up.

Statistical Analysis – Functional measures: To analyze these data, we will examine change in cognitive test scores from baseline over time using mixed-effects regression models, adjusting for level of vision and hearing impairment as fixed or random effects, and compare across sensory group (VI/DSI/Control). The analyses will include consideration of potential moderators or confounders (i.e., gender, age, education). In addition, we will calculate effect sizes, confidence intervals and Bayes Factors for main effects, interactions, and all post-hoc analysis.

When reflecting on the question of a control group we further consulted with the rehabilitation centres and discussed recruitment approaches and limitations; however, for practical and ethical reasons we are not able to withhold rehabilitation services from a possible comparison group, and waiting times are too varied across the centers and seasons of the year to allow for a waiting-list control group. As a result, we are proposing a quasi-experimental repeated-measures design with the intent to let the participants act as their own comparison across time points.

In addition, the data allow us to follow potential **exploratory avenues of analysis:**

- 1) If the recruited participants naturally divide into individuals whose reading effort was reduced and their reading activity has increased, versus those where we do not observe a change in reading behaviour, we can compare these two groups directly (e.g., while still considering their hearing status, or their gender)

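### Objective 2 screens for potential mediators, moderators and confounders by outcome correlation alone, which is insufficient for any of the three roles and has no stated multiplicity control

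*Combined protocol and SAP*

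**What the plan says.** The list of objectives has two entries. The second is: "Correlate participant characteristics with all cognitive outcome variables in order to identify potential mediators, moderators or confounders".

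The design section states: "We will employ a quasi-experimental approach (non-randomized, pre-post intervention study". There are three groups (vision impairment, dual sensory impairment, controls) and three time points.

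The section on statistical analysis of functional measures plans mixed-effects models for change in cognitive scores. These adjust for severity of vision and hearing loss and compare the three groups. On covariates it says: "The analyses will include consideration of potential moderators or confounders (i.e., gender, age, education"). It promises effect sizes, confidence intervals and Bayes factors, including for interactions. It does not say which covariate has which role. It gives no characteristic-by-time interaction apart from what the group comparison implies, and no mediation model.

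Other sections bear on the same roles:
- The third hypothesis links reduced reading effort and improved reading behaviour to cognitive gain at 6 months, maintained at 12.
- The exploratory analyses offer a comparison of participants whose reading did and did not change, reading measures as covariates, and a latent factor analysis.
- The limitations section speculates that benefit may depend on cognitive status at entry.
- The section on sex and gender expects gender to bear on the uptake of assistive technology, and treats gender as a control in all analyses.
- False discovery rate control is stated only for the cortical thickness regions.

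**The concern.** The three roles named in Objective 2 are different, and none is defined by correlation with the outcome.
- A moderator changes the size of the effect. Here that means an interaction with time, or with group and time.
- A mediator lies on the path from rehabilitation to cognition. It must change after the intervention and before the outcome it is meant to explain.
- A confounder must be related to group (or to reading change) as well as to the outcome.

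The objective's stated method checks one condition for confounding and nothing specific to the other two. The study is not randomised, so readers will look to this objective to learn who benefits and which group differences need adjustment. A list of significant correlations could be reported as an answer to those questions when it is not one. The list could also be long: the characteristics section covers psychological, hearing and chart variables, and the chart list is open-ended.

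**Working it through.** **1. The plan's own figure.** The documents give no sample size or error rate for Objective 2. The only calculation is for the main design: "Using a 3x3 (group x time point) within-between design for Analysis of Variance", "with an alpha of 0.05 and a desired power of .95", with the result that "a sample size of $n = 141$ allows us to detect small effect sizes of .15 or greater". Read 0.15 as Cohen's f and take the group by time interaction with k = 3 groups and m = 3 visits. Assume a correlation of 0.5 between repeated measures and sphericity, as neither is stated.
- λ = f²·N·m/(1 − ρ) = 0.0225 × 141 × 3/0.5 = 19.035
- df1 = (k − 1)(m − 1) = 4; df2 = (N − k)(m − 1) = 276
- Power at N = 141 is 0.952. The smallest N reaching 0.95 is 140, or 141 in three equal groups.

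The figure reproduces. It covers the group by time interaction only, and gives no assurance for interactions with further characteristics.

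**2. Can an outcome correlation miss a moderator?** Illustrative model with two equal groups (A = 0 or 1), a characteristic Z with variance 1 and error variance 1: Y = −0.25·Z + 0.5·A·Z + e.
- The slope is −0.25 in one group and +0.25 in the other, so Z is a strong moderator.
- Cov(Z, Y) = −0.25 + 0.5 × 0.5 = 0, so the overall correlation is 0. A simulation with 200,000 subjects gave −0.002 overall, and −0.25 and +0.24 within groups.

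The screen misses it. Moreover, a correlation at Time 1 is taken before rehabilitation, so by itself it cannot show moderation of the response.

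**3. Can it flag a variable with none of the roles?** Model: Y = 0.5·Z + 0.3·A + e, with Z unrelated to A.
- Var(Y) = 0.25 + 0.09 × 0.25 + 1 = 1.2725, so r = 0.5/√1.2725 = 0.44. The simulation gave 0.44, with a Z–A correlation of −0.001.
- "We expected an attrition rate of around 10% at each time point", so 200 × 0.9 × 0.9 = 162 would remain after two losses. At N = 162 the two-sided 0.05 threshold is |r| = 0.154.

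Z is flagged, yet it is only prognostic.

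**4. Chance hits.** The cognitive outcomes section gives at least 5 scores: RAVLT, letter-number sequencing, listening span, choice reaction time and MoCA. All are repeated at 3 visits. The number of characteristics is not stated, so 10 to 20 is an assumption, with the 3 named covariates as the lower bound. The 0.05 threshold is also assumed. With no true association, expected hits = 0.05 × tests, and the chance of at least one hit, if tests were independent, is 1 − 0.95^tests.

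| Characteristics | Scores | Visits | Tests | Expected hits | At least one |
|---|---|---|---|---|---|
| 3 | 5 | 1 | 15 | 0.75 | 54% |
| 10 | 5 | 1 | 50 | 2.5 | 92% |
| 20 | 5 | 1 | 100 | 5 | 99% |
| 3 | 5 | 3 | 45 | 2.25 | 90% |
| 10 | 5 | 3 | 150 | 7.5 | >99% |
| 20 | 5 | 3 | 300 | 15 | >99% |

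The tests are not independent in practice. A null simulation (2,000 runs, N = 162, assumed correlations of 0.3 among characteristics and 0.5 among scores, one visit) gave mean hits of 0.80 for 3 × 5, 2.56 for 10 × 5 and 3.65 for 15 × 5. The chance of at least one was 45%, 81% and 92%. The expected count is essentially unchanged, but the hits cluster.

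**The case against.** The strongest reply is that the objective speaks only of potential mediators, moderators or confounders. It nominates candidates and does not claim to establish roles. Association with the outcome is one condition for confounding, so the step is relevant there. This stands: the method is insufficient, and it would be wrong to call it irrelevant or to say that the objective cannot be met in any form. It does not rescue the screen for moderators, because step 2 shows that a real candidate can be absent from the list.

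A reader might infer that the correlations will choose the model terms, so that the group by time estimates depend on chance. The documents do not say so. The analysis section names gender, age and education, together with vision and hearing severity, and the sex and gender section commits to gender throughout.

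Moderation is also not wholly untested. The contrast of vision-only with dual-impairment participants over time is a test of moderation by hearing category. The exploratory analyses address reading change, although entering reading measures as covariates to remove rehabilitation success conditions on the hypothesised mediator and does not test the path.

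The hit counts rest on an assumed number of characteristics, an assumed threshold and a global null. The plan's own background makes that null unlikely for some pairs, since its pilot data linked reading speed with MoCA. The counts therefore show a scale and do not predict a result.

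Finally, the design section promises a stage 1 pre-registered report. It may supply the missing detail, but it is not among these documents.

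**Conclusion.** The concern holds in a limited form. As stated, Objective 2 uses a screen that can miss true moderators, that flags purely prognostic variables, and that tests neither association with group nor a time-ordered path. No other section adds a characteristic-by-time interaction beyond the group contrast, a time-ordered mediation model, or multiplicity control for the functional outcomes.

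The scale, with no true association and a 0.05 threshold, is 0.75 expected chance hits if only the three named covariates are correlated once with five scores. With 10 to 20 characteristics it is 2.5 to 5 at one visit and 7.5 to 15 over three visits. The number of characteristics, the threshold and the use of all three visits are assumptions.

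It would go too far to conclude that the main group by time results are compromised, since nothing in the documents makes those models depend on the correlations. What is at stake is the interpretation of the second objective.

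**What to change.** - Reword Objective 2 so that it explores named moderators and, if wanted, one mediation path, and describes other associations.
- Keep age, gender and education as prespecified adjustment terms in every model, justified on subject-matter grounds and not by correlation with the outcome.
- Name a short list of moderators, for example baseline MoCA and gender, for which the limitations and sex and gender sections already give a rationale. Test each as an interaction with time (and group) in the planned mixed model. Label these tests exploratory, because the sample size covers only the 3x3 interaction. Do not use baseline MoCA as a moderator of MoCA itself, where regression to the mean would complicate the reading. Hearing category need not be added, as it is largely aliased with group.
- If mediation is examined, use reading change from Time 1 to Time 2 as a predictor of Time 3 cognition, adjusted for baseline cognition. This keeps the time order and fits the hypothesis that 6-month gains are maintained. Cognitive change from Time 2 to Time 3 could be near zero even if that hypothesis is true.
- List the remaining characteristics in advance, label their correlations exploratory, and apply the false discovery rate approach already used for cortical thickness.

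The cost is some rewording, a few additional exploratory terms with low power, and fewer nominally significant correlations. No data are needed beyond those already scheduled. The planned pre-registered report is a natural place for the text.

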To subjectively assess reading effort, we will administer a reading habit questionnaire, a measure developed specifically to evaluate the extent and frequency to which an individual engages in reading activities during their activities of daily living, including reading for entertainment or education. This measure has previously been employed by our team³⁹ and includes questions on language background (e.g., mother tongue, language proficiency), assessed self-reported proficiency in reading (1=no ability, 5=fluent ability), and reading habits before and after onset of low vision (e.g., frequency, enjoyment, type of reading). In addition, participants will be asked to read English or French paragraphs from the

International Reading Speed Test (IReST)⁷⁷. It includes reading comprehension questions that have previously been developed and used in our lab in the context of a low vision reading evaluation using the iPad as a magnification device³⁹. They will also read the English or French version of the MNRead chart⁷⁸, a clinical assessment chart that allows for the measurement of reading acuity (smallest print read), reading speed (in words per minute), critical print size (smallest print at which reading speed is still optimal), and the Reading Accessibility Index⁷⁹, which considers reading ability over a range of print sizes. Finally, we administer a primed lexical decision task where the participant first reads a sentence (prime) and then decides on a word (target) as quickly and as accurately as possible. This task evaluates reading speed, vocabulary comprehension and ability to judge content congruency^{80,81}.

Measures of Participant Characteristics

Depression, Anxiety, Stress: Not surprisingly, the onset of age-related vision loss due to AMD is often accompanied with a multitude of emotional responses that can potentially interfere with the success of low vision rehabilitation. Therefore, the Depression, Anxiety and Stress Scale⁸² will be included in the protocol in order to identify individuals whose rehabilitation outcomes might be influenced by their psychological state. This 21-item questionnaire shows exquisite psychometric properties and has been validated in both English and French⁸³.

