- 2) If no such clear division occurs but participants naturally distribute along a continuum of reading effort and reading behaviour variables, we can simply use the reading measure(s) as co-variables to test whether any/all of the reading effort measures emerge as significant co-variables, and examine whether cognitive scores improved over time across our three groups, after removing the effect of reading rehabilitation success.
- 3) Finally, we will use **latent factor analysis** to explore whether specific clusters of variables are specifically associated with improvements in cognitive functioning and/or improved reading ability. This analysis will be led by [name], together with [name] and [name].

Statistical Analysis - Cortical thickness:

Regression analyses of visual impairment on cortical thickness will be investigated at each vertex of the cortical surface using general linear modeling. Cortical thickness will be modeled as a function of group by controlling for the effects of age, gender, and education. Resulting clusters will be considered significant at $p < 0.05$ using a Monte-Carlo simulation approach. Similar analyses will be performed for cortical volume and cortical surface area, with the addition of total intracranial volume as a nuisance factor¹¹². In addition, a region-of-interest approach will be used to extract the CT values in specific regions of interest using the Destrieux cortical atlas¹¹³ in FreeSurfer. More specifically, we will compare across groups CT values extracted within specific regions of the visual cortex including the

[name]

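### Hypothesis 1 on reading is worded as a before-and-after change and the written three-group model covers only cognitive scores, so retest gain on reading tests could be credited to rehabilitation

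*Combined protocol and SAP*

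**What the plan says.** The first item under Hypotheses covers self-reported reading effort and objective reading speed. It predicts that these "will be statistically significantly reduced after participants have received strategies and tools to facilitate reading". No comparator is named. The last cortical-thickness hypothesis, by contrast, predicts a change in the low vision groups that the control group does not show.

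Under Study Design, the 3x3 layout "will allow us to examine whether cognitive performance will change before and after 6 and 12 months of a low vision reading intervention". Under Statistical Analysis – Functional measures, the model sentence reads "we will examine change in cognitive test scores from baseline over time using mixed-effects regression models", with a comparison across VI, DSI and control. The same section explains why an untreated patient group or a waiting-list group is not possible, and adopts a repeated-measures design "with the intent to let the participants act as their own comparison across time points".

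Reading is tested repeatedly. At 6 and 12 months the research assistant meets each participant, and "all reading, cognitive and hearing measures will be administered each time". The battery under Reading Outcome Measures is a reading habit questionnaire, IReST paragraphs with comprehension questions, the MNRead chart and a primed lexical decision task.

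In the functional analysis, reading measures then appear in three exploratory avenues. The first uses them to split participants. The second uses them as covariates ("we can simply use the reading measure(s) as co-variables to test whether any/all of the reading effort measures emerge as significant co-variables"). The third is a latent factor analysis that looks for variables associated with better cognition, better reading ability, or both.

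**The concern.** Only patients receive rehabilitation, so a change judged after its receipt is a change within patients. That change mixes the rehabilitation effect, familiarity with the tests after up to three administrations, and the course of the AMD. The documents mention neither practice effects nor parallel reading forms, and plan no patient-versus-control test of reading change. Control reading data appear to be collected at the same visits.

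Hypothesis 1 is the first link in the study's argument: rehabilitation makes reading easier, and easier reading benefits cognition. If a shared retest gain can confirm that link, a significant result does not show that rehabilitation improved reading.

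**Working it through.** **1. The plan's own figure.** Sample Size gives n = 141 for a 3x3 within-between ANOVA with effect size .15, alpha 0.05 and power .95. Read .15 as Cohen's f, and assume visit correlation ρ = 0.5 and sphericity, since the plan states neither. For the group-by-time interaction:

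- λ = f²·N·m/(1−ρ) = 0.0225 × 141 × 3 / 0.5 = 19.04
- df = (3−1)(3−1) = 4 and (141−3)(3−1) = 276
- power = 0.952; the minimum N is 140, or 141 for three equal groups

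The figure therefore reproduces as a group-by-time test, a contrast that the analysis text does not assign to reading outcomes.

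**2. Completers.** The plan has 150 patients and 50 controls, with about 10% attrition at each time point. Compounding over two follow-ups gives 150 × 0.81 = 121.5 and 50 × 0.81 = 40.5.

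**3. Before-and-after test in patients, no true effect.** Let g be the retest gain in baseline SD units. The SD of change is s = √(2(1−ρ)), which is 1.000 at ρ = 0.5 and 0.775 at ρ = 0.7. The noncentrality is g√n/s, the test is a two-sided 5% one-sample t, and n = 121.5. Both g and ρ are assumptions.

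| g | ρ | noncentrality | chance of a significant result |
|---|---|---|---|
| 0.1 | 0.5 | 0.1 × 11.02 / 1.000 = 1.10 | 19% |
| 0.2 | 0.5 | 2.20 | 59% |
| 0.1 | 0.7 | 0.1 × 11.02 / 0.775 = 1.42 | 29% |
| 0.2 | 0.7 | 2.85 | 81% |

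Simulation with 20,000 replicates and 121 patients agrees: 19%, 59%, 29% and 81%.

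**4. Patient-minus-control difference in change.** If both groups have the same gain, it cancels and the test rejects about 5% of the time (simulated 4.9–5.1% at these settings). That follows from the assumption of equal gains.

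For a true effect d, the noncentrality is d / (s√(1/121.5 + 1/40.5)), where the root is 0.181:

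| d | power, ρ = 0.5 | power, ρ = 0.7 |
|---|---|---|
| 0.2 | 19% | 29% |
| 0.5 | 78% | 94% |
| 1.0 | over 99% | over 99% |

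The same table shows what happens when gains are unequal. If patients gain 0.2 SD more from retesting than controls and rehabilitation does nothing, the contrast is significant 19–29% of the time.

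**5. Cost in detectable effect.** With 121 and 40 completers, the smallest difference in change detectable with 80% power is (1.960 + 0.842) × s × √(1/121 + 1/40) = 0.51 SD (ρ = 0.5) or 0.40 SD (ρ = 0.7). The one-group test detects 0.26 or 0.20 SD.

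**The case against.** The strongest reply is that a hypothesis is not an analysis plan. No test of Hypothesis 1 is written, so a reader who infers that the authors have chosen a pre-post test goes beyond the text. That stands. Reading is listed among the outcome measures, and the heading Functional measures could be meant to include it, together with the comparison across groups and the interactions mentioned there. The sentence under that heading names only cognitive scores, however, so the point is at best ambiguous, and one sentence would settle it.

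A reader might also infer that the cognitive results can no longer be interpreted through reading. The documents do not support that. Hypothesis 3 compares participants whose reading effort fell with those whose effort stayed high. A gain common to everyone leaves their ranking unchanged and is absorbed by the intercept when reading change is a linear covariate. The cognitive model also has its own controls.

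The controls are an imperfect yardstick. They have age-normal vision, may read near a ceiling, may gain differently from retesting and do not reflect AMD progression, which could hide a benefit in patients. This stands, and it means the 5% error rate is a best case for the contrast.

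The plan also cites strong evidence that rehabilitation improves reading, so a true effect of zero may be unlikely. Even so, a retest gain would inflate the estimate, and the effect-size range quoted under Sample Size starts at d = .20. Whether the same IReST paragraphs are reused is not stated, and the point does not rely on it.

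Finally, the plan is open about its pre-post design and says the analysis will go to a stage 1 pre-registered report. That is the natural place to make the repair.

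**Conclusion.** The point holds as a gap between hypothesis and analysis. Hypothesis 1 is worded as a before-and-after change, the written group comparison covers cognitive scores only, and no patient-versus-control test of reading change is planned. If the wording is followed, any retest gain counts as rehabilitation benefit. The rates of 19–59% (ρ = 0.5) and 29–81% (ρ = 0.7) rest on assumed gains of 0.1–0.2 SD, assumed correlations, a true effect of zero and about 121 patient completers. They illustrate how sensitive the pre-post test is; they do not show that a gain of this size will occur. Disease progression could push the pre-post estimate the other way. The repair is worth making because it is cheap and Hypothesis 1 carries the first step of the argument.

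**What to change.** Under Statistical Analysis – Functional measures, name the reading measures as outcomes of the same mixed model with group, visit and group-by-visit terms: IReST speed, MNRead speed, the Reading Accessibility Index, lexical decision, and those self-report items that apply to controls.

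- Report the patient-minus-control difference in change beside the within-patient change. Attribute reading improvement to rehabilitation only where it exceeds control change, and word Hypothesis 1 to match.
- Some questionnaire items, such as habits before and after the onset of low vision, do not apply to controls. For these, report within-patient change without a causal claim.
- Define control visit timing. Follow-up is counted from the initial rehabilitation appointment, which controls do not have; 6 and 12 months from Time 1, or from a matched date, would serve.
- Correct the direction. The hypothesis predicts a reduction in reading speed, whereas improvement is an increase.

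This needs no new participants or tests. The costs are the lower power for small effects shown above and dependence on normally sighted controls, so the write-up should say that the contrast reduces retest bias and does not remove it.
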